8.9.9.1. Columbia-Suicide Severity Rating Scale (C-SSRS)

Patients ≥ 6 years of age

As required in the US by the Food and Drug Administration (FDA), for clinical trials of CNS-acting medications, changes in suicidality as assessed by the C-SSRS will be monitored over the course of the trial to ensure patient safety.

The C-SSRS is a tool used not only to predict suicide attempts but to assess the full range of evidence-based ideation and behavior items, with criteria for next steps (e.g., referral to a MPH). There are 2 versions of the C-SSRS that will be administered according to the SoA (Table 1 and Table 2):

- The Baseline/Screening version of the scale is the initial form of the instrument to assess suicidality in a patient's lifetime. This version can assess a patient's lifetime suicidality for data collection purposes as well as eligibility based on inclusion/exclusion criteria.

- The Since Last Visit version of the scale assesses suicidality since the patient's last visit. This version is meant to assess patients who have completed at least 1 initial C-SSRS assessment and should be used in subsequent visits. The 'Since Last Visit' version of the C-SSRS is asking about any suicidal thoughts or behaviors the patient/participant may have had since the last time the C-SSRS was administered.

To be eligible for the trial, a patient cannot have a suicidal ideation of type 4 or 5, a suicide attempt during the patient's lifetime, or any suicidal behavior in the last month.

Any patient with a suicidal behavior or a suicidal ideation of type 4 or 5 on the CSSRS will be referred to a mental health professional.

8.9.9.2. Patient Health Questionnaire -9 (PHQ-9)

The PHQ-9 is a 9-item depression scale of the Patient Health Questionnaire. The PHQ-9 is a tool for assisting clinicians in diagnosing depression as well as selecting and monitoring treatment. After the patient has completed the PHQ-9 questionnaire, it is scored by the trial staff. The PHQ-9 will be administered in patients ≥ 12 years of age or according to the SoA (Table 1 and Table 2).

Any patient with a PHQ-9 score ≥ 10 will be referred to a mental health professional.

8.9.9.3. Children's Depression Inventory-2

The CDI-2 has both a self-report and a parent version. The CDI-2: Self-Report Short version is an efficient screening measure that contains 12 items and takes about 5-10 minutes to administer. The self-report short version will be administered to patients < 12 years of age according to the SoA (Table 1 and Table 2).

Items on the CDI-2 Parent form correspond to items on the self-report version and are suitably rephrased. Item selection for the parent forms was guided to maximize validity, and thus focused on observable manifestations of depression. The CDI-2 parent form consists of 17 items and the 4 choices provided for each item correspond to 4 levels of symptomatology: 0 (not at all), 1 (some of the time), 2 (often), or 3 (most of the time). The CDI-2 parent version will be administered to caregivers of patients < 12 years of age according to the SoA (Table 1 and Table 2).

Any patient with a CDI-2 score > 20 will be referred to a mental health professional.

8.9.10. Overdose

One accidental overdose has been reported in the clinical program in a pediatric patient receiving a 5-mg dose instead of a 0.5-mg dose. The patient had mild symptoms that resolved.

In the event of an overdose, the Investigator should contact the Medical Monitor immediately. Appropriate supportive treatment should be initiated according to the patient's clinical signs and symptoms.

The quantity of the excess dose as well as the duration of the overdose are to be documented in the eCRF.

Decisions regarding dose interruptions or modifications will be made by the Investigator in consultation with the Sponsor based on the clinical evaluation of the patient.

8.9.11. Adverse and Serious Adverse Events

Adverse events will be reported by the patient (or, when appropriate, by a caregiver, surrogate, or the patient's legally authorized representative).

The Investigator and any designees are responsible for detecting, documenting, and recording events that meet the definition of an AE or SAE and remain responsible for following-up AEs that are serious, considered related to the trial treatment or trial procedures, or that caused the patient to discontinue trial treatment (see Section 6.3).

Details on recording AEs and SAEs, including definitions, are provided in [Appendix 5](#).

8.9.11.1. Time Period and Frequency for Collecting AE and SAE Information

All AEs, including SAEs, will be collected from the time informed consent is signed until the EOS visit at the time points designated in the SoA ([Table 1](#) and [Table 2](#)). AEs reported after dosing on Day 1 will be considered TEAEs.

Medical occurrences that begin before the start of trial treatment but after obtaining informed consent will be recorded on the Medical History/Current Medical Conditions section of the eCRF, not in the AE section.

All SAEs will be recorded and reported to the Sponsor or designee within 24 hours without undue delay but no later than within 24 hours, as indicated in [Appendix 5](#). The Investigator will submit any updated SAE data to the Sponsor without undue delay but no later than within 24 hours of it being available.

Investigators are not obligated to actively seek AE or SAE information from former trial patients. However, if the Investigator learns of any SAE, including a death, at any time after a patient has been discharged from the trial, and he/she considers the event to be reasonably related to the trial treatment or trial participation, the Investigator must promptly notify the Sponsor.

The method of recording, evaluating, and assessing causality of AEs and SAEs and the procedures for completing and transmitting SAE reports are provided in [Appendix 5](#).

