1. SYNOPSIS

Name of Sponsor/Company: Rhythm Pharmaceuticals, Inc.	
Name of Investigational Product: Setmelanotide	
Title of Trial: A 2-Stage (Open-Label Followed by Randomized Double-Blind, Placebo-Controlled Stage), Phase 2 Trial of Setmelanotide in Patients with Specific Gene Variants in the Melanocortin-4 Receptor Pathway	
Trial center(s): Approximately 80 centers in North America, Europe and the Middle East	
Studied period (years): Estimated date first patient enrolled: 4 th Quarter (Q4) 2021 Estimated date last patient completed: Q4 2024	Phase of development: 2
Objectives: Primary: 
To evaluate the proportion of patients with obesity with genetic variants in a specific gene in the melanocortin-4 receptor (MC4R) pathway who achieve a clinically meaningful reduction in body weight in response to setmelanotide at the end of open-label treatment Secondary: 
To evaluate change in weight parameters and hunger in response to setmelanotide in patients with genetic variants in a specific gene in the MC4R pathway at the end of open-label treatment [REDACTED]	
Safety: 
To evaluate the safety and tolerability of setmelanotide in patients with genetic variants in the MC4R pathway	
Methodology: This is a 2-stage (open-label stage followed by a randomized double-blind, placebo-controlled stage) Phase 2 trial of setmelanotide in patients with obesity with specific gene variants in the MC4R pathway.	

Screening

The Screening Period begins with signing the informed consent/assent form and will last between 2 and 8 weeks. During the Screening Period, patients will undergo all procedures as outlined in the Schedule of Assessments (SoA) Stage 1 (Table 1) to determine if they meet the Inclusion and Exclusion criteria.

During the Screening Period, patients will undergo medical evaluation and they or their caregivers will receive training on injection of trial medication and other trial procedures. Patients (or their caregivers) will be issued an electronic diary to capture daily compliance with injections (post enrollment) and hunger score assessments (starting during Screening).

Stage 1 (Open-Label)

Stage 1 of the trial begins with the enrollment visit (Study Day 1).

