APPENDIX 4. INJECTION SITE EVALUATIONS

Injection sites will be assessed at the time points outlined in the Schedule of Assessments (Table 1 and Table 2), and in the setting of any injection site reaction adverse experience. This assessment will consider severity and measurement (length and width if applicable) of any instance of erythema, edema, induration, itching, pain/tenderness or other relevant findings.

Local Skin Tolerability Assessment

Reaction	NONE	Mild	Moderate	Severe	Measurement (if applicable)
Erythema* ¹					
Edema*					
Induration* ¹					
Itching					
Pain or Tenderness					
Other: _____					

* If present, region will be measured, length and width as appropriate.

¹ In the event of severe erythema, defined as ≥ 10 cm, and/or induration of the injection area of the size of ≥ 10 cm and in the presence of fever defined as $\geq 38^{\circ}\text{C}$, or based on the Investigator's clinical judgement, the Investigator should contact the Sponsor and discuss therapeutic management of the patient and potential temporary drug discontinuation.

Initials: _____

APPENDIX 5. ADVERSE EVENTS: DEFINITIONS AND PROCEDURES FOR RECORDING, EVALUATING, FOLLOW-UP, AND REPORTING

Definition of Adverse Event (AE)

AE Definition

• An AE is any untoward medical occurrence in a patient or clinical trial patient, temporally associated with the use of trial treatment, whether or not considered related to the trial treatment.• NOTE: An AE can therefore be any unfavorable and unintended sign (including an abnormal laboratory finding), symptom, or disease (new or exacerbated) temporally associated with the use of trial treatment.

Events Meeting the AE Definition

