If an event is not an AE per definition above, then it cannot be an SAE even if serious conditions are met (e.g., hospitalization for signs/symptoms of the disease under study, death due to progression of disease).

A SAE is defined as any untoward medical occurrence that, at any dose:

a. Results in death

b. Is life-threatening

The term ‘life-threatening’ in the definition of ‘serious’ refers to an event in which the patient was at risk of death at the time of the event. It does not refer to an event, which hypothetically might have caused death, if it were more severe.

c. Requires inpatient hospitalization or prolongation of existing hospitalization

In general, hospitalization signifies that the patient has been detained (usually involving at least an overnight stay) at the hospital or emergency ward for observation and/or treatment that would not have been appropriate in the physician’s office or outpatient setting. Complications that occur during hospitalization are AEs. If a complication prolongs hospitalization or fulfills any other serious criteria, the event is serious. When in doubt as to whether “hospitalization” occurred or was necessary, the AE should be considered serious.

Hospitalization for elective treatment of a pre-existing condition that did not worsen from baseline is not considered an AE.

d. Results in persistent disability/incapacity

- The term disability means a substantial disruption of a person’s ability to conduct normal life functions.
- This definition is not intended to include experiences of relatively minor medical significance such as uncomplicated headache, nausea, vomiting, diarrhea, influenza, and accidental trauma (e.g., sprained ankle) which may interfere with or prevent everyday life functions but do not constitute a substantial disruption.

e. Is a congenital anomaly/birth defect

A SAE is defined as any untoward medical occurrence that, at any dose:

f. Important medical event

- Medical or scientific judgment should be exercised in deciding whether SAE reporting is appropriate in other situations such as important medical events that may not be immediately life-threatening or result in death or hospitalization but may jeopardize the patient or may require medical or surgical intervention to prevent one of the other outcomes listed in the above definition. These events should usually be considered serious.

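### Protocol 8.9.11.1 is internally inconsistent on events between consent and first dose: AEs and SAEs are collected from consent, but pre-dose events go to medical history with no exception for serious or procedure-related ones, and TEAE status follows report time

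*Protocol*

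**What the plan says.** Protocol Section 8.9.11.1 contains four statements that bear on this interval.

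- Collection period: "All AEs, including SAEs, will be collected from the time informed consent is signed until the EOS visit". The Stage 1 Schedule of Assessments (Table 1) agrees, since its adverse-event row is marked at Screening.
- TEAE rule: "AEs reported after dosing on Day 1 will be considered TEAEs".
- Recording location: occurrences that begin after consent but before trial treatment "will be recorded on the Medical History/Current Medical Conditions section of the eCRF, not in the AE section".
- Expedited reporting: "All SAEs will be recorded and reported to the Sponsor or designee within 24 hours", with a pointer to Appendix 5. The sentence gives no start point of its own.

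Appendix 5 defines an AE as an untoward occurrence "temporally associated with the use of trial treatment, whether or not considered related to the trial treatment". Its SAE definition opens with a gate: "If an event is not an AE per definition above, then it cannot be an SAE even if serious conditions are met". It also counts as an AE a condition first detected after dosing, even where the condition may predate the trial.

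The Synopsis fixes the length of the interval: "The Screening Period begins with signing the informed consent/assent form and will last between 2 and 8 weeks".

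**The concern.** The same interval has two recording rules. A site is told to assess AEs at Screening and to collect them from consent. It is then told to keep every occurrence that begins in that interval out of the AE section. The medical-history sentence carves out neither serious events nor events caused by trial procedures, although screening includes blood sampling and, under Exclusion Criterion 12, biopsy of any concerning skin lesion. Section 8.9.11 makes investigators responsible for following AEs related to trial procedures, which implies that such events belong in the AE record whenever they occur.

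Two things are at stake. The first is whether a serious event in screening, particularly one caused by a procedure, is recorded and sent to the sponsor in the same way at each of about 80 centers. The second is whether an event that began before treatment can be counted as emerging on treatment.

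**Working it through.** No sample-size or error-rate calculation applies. The check is one of consistency, with a single figure to reproduce.

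**Length of the interval.** Table 1 places Screening at Study Day -56 to -14. 56 / 7 = 8 weeks and 14 / 7 = 2 weeks, which matches the 2 to 8 weeks in the Synopsis.

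**Where a pre-dose event is recorded.**

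| Source | Answer for an event with onset between consent and first dose |
|---|---|
| 8.9.11.1, collection sentence | Collected as an AE or SAE |
| Table 1, adverse-event row | Assessed at Screening |
| 8.9.11.1, medical-history sentence | Medical history only; no exceptions |
| 8.9.11, investigator responsibilities | AEs related to trial procedures are followed; no restriction to the treatment period |

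The third row cannot be carried out together with the other three for a serious or procedure-related event.

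**Whether a pre-dose serious event is reportable.** Two readings are open.

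- *Reading A.* SAEs are collected from consent, and all SAEs go to the sponsor within 24 hours. A screening SAE is therefore reportable, and the medical-history sentence affects only where it sits in the eCRF.
- *Reading B.* The 24-hour sentence covers SAEs as set out in Appendix 5. Appendix 5 requires an AE to be associated in time with use of trial treatment and says that what is not an AE cannot be an SAE. Before the first dose there has been no use of trial treatment. The event is therefore not an SAE, goes to medical history, and does not trigger the 24-hour rule.

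Nothing in Section 8.9.11.1 or Appendix 5 says which reading prevails.

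**Time basis of the TEAE rule.** Take an event that starts during screening and is first mentioned at the Day 14 virtual visit.

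- The medical-history sentence turns on onset ("Medical occurrences that begin before the start of trial treatment but after obtaining informed consent will be recorded on the Medical History/Current Medical Conditions section"). Onset was before treatment, so the event is medical history.
- The TEAE sentence turns on reporting. The report came after dosing on Day 1, so the event is a TEAE.
- Appendix 5 adds to the overlap by accepting as AEs conditions detected after dosing that may already have been present.

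**What the visible SAP adds.** Section V.C assigns events before randomization to Stage 1 and sets no lower bound at first dose. Section V.E sets a start date that lacks only the day, in the month of first dose, to the first-dose date. Neither rule settles how a screening-onset event is classified. The SAP places its adverse-event definitions in Section IX.B, and the opening of that section is not in the public text.

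**The case against.** The strongest reply is that the protocol already covers a screening SAE. Collection starts at consent, all SAEs are reported within 24 hours, and the medical-history sentence names an eCRF location without suspending any reporting duty. The examples attached to the Appendix 5 gate concern hospitalization or death from the disease under study, so it was probably not written with pre-dose events in mind. This largely stands. A reader might infer that the protocol leaves serious screening events without a reporting route, or excludes them from reporting. The documents do not support that: Reading A is available and is arguably the more natural one. What remains is that Reading B follows from the literal definitions and no sentence rules it out.

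The second reply is that a TEAE must first be an AE, so an event routed to medical history never reaches the TEAE rule, and that the SAP governs the tables in any case. This stands in part. A reader might infer that the TEAE tables will be wrong. That cannot be shown, because the SAP's TEAE definition is not visible and may already use onset; imputing partial AE start dates against the first-dose date would fit such a rule. But the protocol sentence still says *reported*, and the Appendix 5 provision on conditions detected after dosing prevents the sequential reading from being decisive.

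A reader might also gauge the problem by multiplying screening length by enrollment. That measures time spent in screening, not misplaced events, and most new pre-dose conditions can properly stay in medical history.

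**Conclusion.** The point holds as an internal inconsistency in Protocol Section 8.9.11.1, compounded by the definitions in Appendix 5. For events that begin in the 2 to 8 weeks between consent and first dose, the stated rules place serious and procedure-related events outside the AE section while also calling for their collection as AEs and SAEs. Failure to report a serious screening event is a risk under one literal reading, not something the protocol directs. The mismatch between report time and onset is plain in the protocol text. Its effect on the TEAE tables is possible but not established.

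The documents give no rate for serious or procedure-related events in screening, so the number affected cannot be estimated; it is likely to be small. The primary endpoint, a BMI response at the end of Stage 1, is not affected. The correction is worth making because safety is a stated objective and the change is only a few words.

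**What to change.** 1. In Section 8.9.11.1, exempt serious events and events related to trial procedures from the medical-history sentence. Record them on the AE/SAE form, flagged as non-treatment-emergent, and state that the 24-hour SAE rule applies from consent. Other new conditions that begin before the first dose stay in medical history.
2. Replace the report-time criterion for TEAEs with onset or worsening on or after the first dose, and check that SAP Section IX.B uses the same definition.
3. Amend the Appendix 5 AE definition so that it is consistent with collection from consent.

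The cost is a protocol clarification, matching eCRF completion guidance and a few more AE/SAE forms. Treatment, visits and sample size do not change.

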8.9.11.2. Method of Detecting AEs and SAEs

Care will be taken not to introduce bias when detecting AEs and/or SAEs. Open-ended and non-leading verbal questioning of the patient is the preferred method to inquire about AE occurrences.

8.9.11.3. Follow-up of AEs and SAEs

After the initial AE/SAE report, the Investigator is required to proactively follow each patient at subsequent visits/contacts. All SAEs will be followed until resolution, stabilization, the event is otherwise explained, or the patient is lost to follow-up. Further information on follow-up procedures is given in [Appendix 5](#).

8.9.11.4. Regulatory Reporting Requirements for SAEs

- Prompt notification by the Investigator to the Sponsor of an SAE is essential so that regulatory obligations and ethical responsibilities towards the safety of patients and the safety of a trial treatment under clinical investigation are met.
- The Sponsor has a legal responsibility to notify both the local regulatory authority and other regulatory agencies about the safety of a trial treatment under clinical investigation. The Sponsor will comply with country-specific regulatory requirements relating to safety reporting to the regulatory authority, IRBs, IECs, and Investigators.
- Investigator safety reports must be prepared for suspected unexpected serious adverse reactions (SUSAR) according to local regulatory requirements and Sponsor policy and forwarded to Investigators as necessary.
- An Investigator who receives an Investigator safety report describing a SAE or other specific safety information (e.g., summary or listing of SAEs) from the Sponsor will review and then file it along with the Investigator Brochure and will notify the IRB/IEC, if appropriate according to local requirements.

9. SAFETY DATA MONITORING

The Investigators will be responsible to review and evaluate safety data from their patients in a continuous manner. Cumulative safety data from the trial will be reviewed by the Sponsor on an ongoing basis for any safety signals or tolerability concerns. Additionally, this trial will be monitored by an independent Data Safety Monitoring Board (DSMB). The DSMB will operate under a separate charter and will meet periodically (e.g., every 3 months) to review the cumulative safety data from the trial and will make a recommendation to continue or modify the trial, if needed.

10. STATISTICS

This section describes the plans for analysis of the trial data. Details of the statistical methodology for summaries and statistical analyses will be provided in a separate statistical analysis plan (SAP), which will be maintained by the Sponsor. The SAP may modify the plans outlined in the protocol; however, any major modifications of the primary endpoint definition and/or its analysis will also be reflected in a protocol amendment. If, after the trial has completed, changes are made to the SAP, then these deviations to the plan will be listed, along with an explanation as to why they occurred, in the clinical study report for the trial, as appropriate.

10.1. Sample Size Determination

The trial is a 2-stage design: Stage 1 is open-label treatment part, and Stage 2 is randomized, double blind, placebo-controlled part. It is planned to enroll 100-200 patients in the trial. Sample size is not based on any statistical considerations.

